17.2 Secondary Outcome Measures

1) HIV outcomes:

- a) HIV-1 RNA viral suppression (plasma HIV-1 RNA pcr \leq 200 copies/mL) at 16 weeks compared with screening (binary, laboratory assay).
- b) Change in CD4 count at the week 16 visit compared with screening (count; laboratory measurement).

2) Substance Use:

- a) Change in 30 day opioid abstinence (by Addiction Severity Index (ASI)-lite self-report, TLBF (self-report) and urine drug screen (UDS) confirmation) in the final 30 days of the 16 week trial compared to screening (binary; laboratory data and self-report).
- b) Change in past 30-day alcohol and other drug use by ASI-lite and UDS at week 16 visit compared to screening (binary; laboratory data and self-report).

3) Engagement in HIV Care:

- a) Change in the proportion of participants prescribed ART within 16 weeks following randomization, compared to baseline (binary; medical record abstraction).
- b) Proportion of participants taking 100% of prescribed ART doses in the past 3 days at 16 weeks for those prescribed ART at any point during the 16 week trial (proportion; self-reported ACTG adherence measure).
- c) Number of HIV primary care visits at 16 weeks (count, chart abstraction).

4) Participant safety:

- a) Change in liver enzymes between screening and week 16 visit (laboratory assay).
- b) Any fatal and non-fatal opioid overdose between screening and week 16 visit (binary; medical record abstraction and self-report).
- c) Change in Concise Health Risk Tracking score between screening and week 16 visit (continuous; self-report).
- d) Proportion of participants assigned to XR-NTX who develop precipitated opioid withdrawal.

Sample Size and Duration of Randomized Pilot Study Recruitment Phase

The randomized pilot study will recruit until either 50 participants have been enrolled or 12 months of recruitment have elapsed, whichever comes first. Justification for this decision follows:

The proposal for a phase III randomized trial assumes enrollment of 400 participants from 8 sites in 18 months, implying a recruitment rate of about 2.28 participants per site-month. **Table 17.2.1** explores by simulation the consequences for the precision of various pilot-study-derived estimates of having a pilot study in which per site-month recruitment rate = (1.14, 2.28), number of sites = (1,2), and time period = (12 months, 18 months). **Table 17.2.1** investigates limiting the pilot sample size to 50 participants (n-limited), or limiting the enrollment time to 12 or 18 months (t-limited), or limiting both sample size and recruitment time simultaneously (n- and t-limited). The columns of **Table 17.2.1** headed – “Parameters” depict all the parameter combinations investigated.

5) The notation used in **Table 17.2.1** follows:

- n = pilot study sample size
- t = pilot study recruitment time (months)
- s = number of sites in the pilot study
- rate = recruitment rate (participants per site-month) assumed for both the pilot study and the subsequent phase III randomized trial
- N = randomized trial sample size (assumed to be 400)
- T = randomized trial recruitment time (months). This assumes that the sites in the randomized trial will exhibit the same performance that they did in the pilot study.
- S = number of sites in the randomized trial (this is not actually shown in **Table 17.2.1**, but is assumed to be 8)
- $\hat{T} = \frac{s/n}{S/N} t$, the estimator, derived from the pilot study, of the recruitment time for the subsequent phase III randomized trial
- $p(\text{init})$ = the probability of treatment initiation, which is the chance that a participant who is randomized to one of the two arms within the pilot study will obtain the 1st dose of the treatment. There is one $p(\text{init})$ calculated for each of the two arms.
- $p(\text{ret})$ = the probability of retention, which is the chance that a pilot-study participant who has obtained the 1st dose will still be on treatment at 4 months. There is one $p(\text{ret})$ calculated for each of the two arms.

6) The columns of **Table 17.2.1** headed “Outcomes (Percentiles)” show the consequences for various outcomes, given the parameters controlling the pilot study. Their meanings follow:

- 20% n = the 20th percentile of the sample size of the pilot study. The pilot study will very likely recruit at least this many participants
- 80% t = the 80th percentile of the recruitment time for the pilot study (months). The pilot study will very likely not take longer than this time to recruit.
- 80% $p(\text{init})$ = the 80th percentile of the 95% confidence interval half width for the pilot- study-derived estimate of the probability of treatment initiation. If this value is x , it means that the 95% confidence interval for the estimate of the probability of treatment initiation will very likely not be wider than $\pm x$.
- 80% $p(\text{ret})$ = the 80th percentile of the 95% confidence interval half width for the pilot- study-derived estimate of the probability of treatment retention. If this value is x , it means that the 95% confidence interval for the estimate of the probability of treatment retention will very likely not be wider than $\pm x$. This confidence interval is slightly wider than for $p(\text{init})$ because **Table 17.2.1** assumes 10% attrition between the time of recruitment and initiation.
- 80% T = the 80th percentile of the time to recruit in the subsequent phase III randomized trial.
- 80% $|\hat{T} - T|$ = the 80th percentile of the absolute value of the predictive bias of \hat{T} for T

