Aim 4: Assess the feasibility of integrating XR-NTX for opioid and alcohol use disorders into HIV clinics. Data collection during study start-up will inform selection of 2 HIV clinics to implement XR-NTX treatment. HIV providers and staff will be trained in detoxification and XR-NTX induction and management. HIV-infected subjects with untreated opioid and/or alcohol use disorders will be randomized to XR-NTX or TAU, followed by detoxification (if needed) and treatment induction. The primary outcomes are 1) treatment initiation (successful treatment initiation of XR-NTX or TAU within 4 weeks of randomization), and 2) retention on treatment condition at 16 weeks. Secondary outcomes include change in 1) HIV-1 RNA viral suppression, 2) Illicit drug and alcohol use, 3) HIV care engagement (receipt of ART, HIV visit adherence, ART adherence), and safety (percent with precipitated withdrawal, hepatotoxicity, or overdose).

Aim 4 Pilot Objective A: Estimate effect size point estimates for rate of treatment initiation and 16 week retention among HIV-infected patients with alcohol or opioid use disorders randomized to XR-NTX vs. TAU.

Aim 4 Pilot Objective B: Estimate effect size point estimates for secondary outcomes of HIV-1 RNA viral suppression, illicit drug and alcohol use, HIV care engagement, and safety among HIV-infected patients with alcohol or opioid use disorders randomized to XR-NTX vs. TAU.

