8.2 Secondary Outcome Measures

1) HIV outcomes:

- a) HIV-1 RNA viral suppression (plasma HIV-1 RNA pcr < 200 copies/mL) at 16 weeks compared with screening (binary, laboratory assay).
- b) Change in CD4 count at 16 weeks following treatment initiation compared with screening (count; laboratory measurement).

2) Substance Use:

- a) Change in 30 day opioid abstinence (by Addiction Severity Index (ASI)-lite self-report, Time-Line Follow-Back (TLFB) and urine drug screen (UDS) confirmation) in the final 30 days of the 16 week trial compared to screening (binary; laboratory data and self-report).
- b) Change in past 30-day alcohol and other drug use by ASI-lite, TLFB and UDS at week 16 visit, compared to screening (binary; laboratory data and self-report).

3) Engagement in HIV Care:

- a) Change in the proportion of participants prescribed ART within 16 weeks following randomization, compared to baseline (binary; medical record abstraction).
- b) Proportion of participants taking 100% of prescribed ART doses in the past 3 days at 16 weeks for those prescribed ART at any point during the 16 week trial (proportion; self-reported ACTG adherence measure).
- c) Number of HIV primary care visits at 16 weeks (count, chart abstraction).

4) Participant safety:

- a) Change in liver enzymes between screening and week 16 visit (laboratory assay).
- b) Any fatal and non-fatal opioid overdose between screening and week 16 (binary; medical record abstraction and self-report).
- c) Change in Concise Health Risk Tracking score between screening and week 16 visit (continuous; self-report).
- d) Proportion of participants assigned to XR-NTX who develop precipitated opioid withdrawal.

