9.2.2 Screening and Enrollment Procedures (1-4 weeks duration)

Once a person has completed the Pre-Screening Interview process and meets basic eligibility, they will either be asked to stay for the Screening Visit or scheduled to come back (based on staff and candidate's availability).

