9.2.8 Randomization

We anticipate that the timing of randomization will be variable, but follow shortly after baseline assessments and final confirmation of eligibility. Participants will have up to 4 weeks following randomization to initiate his or her assigned treatment. Success in initiating assigned treatment will be tracked.

Participants will be randomized in a 1:1 fashion to either office-based XR-NTX or TAU using a permuted block design with randomly-sized blocks. Predominance of alcohol vs. opioid use disorder for a given participant will

likely be strongly correlated with primary and secondary outcomes, and this variable will be recorded upon randomization. The severity of opioid and alcohol use disorder will also likely be an important independent predictor of treatment retention and substance use (Sullivan, Rothenberg et al. 2006; Carpenter, Jiang et al. 2009; Brooks, Comer et al. 2010). Participants need not be abstinent from opioids or alcohol at the time of randomization.

The randomization procedure will be conducted in a centralized process through the Data and Statistical Center (DSC). Specifically, randomization schedules will be created by the study statistician for each site. The randomization schedules will be of a randomized-block nature to ensure relative equality of assignment across condition across the recruitment period and to prevent the potential for study staff guessing the next assignment which is heightened when a fixed block-size is used. After the baseline assessment is successfully completed, a designated study staff member will perform the randomization. Randomization for each participant is done over the Internet using the Enrollment Module in AdvantageEDC.

The DSC statistician will review the randomization data on a regular basis to ensure that the scheme is being implemented according to plan. If a participant drops out of the study at any point after randomization, the randomization slot will not be re-allocated to a new participant due to the intent-to-treat nature of the study.

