15.2 Non-Fatal Overdose

Non-fatal overdoses in the past 4 weeks will be assessed using a self-reported instrument used in previous studies at baseline and 16 weeks or the end-of-medication visit (if medication is stopped early) (Coffin, Tracy et al. 2007). Overdose events are sentinel events that are less likely to be prone to recall bias than other events. If non-fatal overdose resulted in adverse event, it should also be captured on the AE/SAE CRF.

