17.5 Analysis of secondary outcomes

The pilot study is small and thus probably under-powered for hypothesis tests. Any conclusions arising from secondary analysis must be regarded as hypothesis-generating only, and need to be validated by independent data. We contemplate no adjustment for multiplicity.

Secondary outcomes will be analyzed as indicated in the italicized text describing each secondary endpoint.

HIV outcomes:

- a) Sustained HIV RNA viral suppression (plasma HIV viral load of < 200 copies/mL) at 16 weeks (*binary, laboratory assay*). *Chi-squared test of independence of sustained viral suppression on treatment assignment.*
- b) Change in CD4 count at 16 weeks following randomization compared with baseline (*count; laboratory measurement*). T-test.

1) Engagement in HIV Care:

- a) Change in the proportion of study participants prescribed ART within 16 weeks following randomization, compared to baseline (*binary; medical record abstraction*). *Each individual can be scored either 0 (not prescribed ART) or 1 (prescribed ART) at both baseline and follow-up, after which his or her outcome score will be the follow-up score minus the baseline score. Outcome scores will be analyzed via rank-based methods such as Wilcoxon rank-sum tests. Covariates can be considered via the cumulative logit model.*
- b) Proportion of participants taking 100% of prescribed ART doses in the past 3 days at 16 weeks for those prescribed ART at any point during the 16 week trial (*proportion; self-reported ACTG adherence measure*). *Chi-squared test comparing proportion to treatment assignment, for those prescribed ART.*
- c) Number of HIV primary care visits at 16 weeks (count, chart abstraction) *outcome scores will be analyzed via rank-based methods such as Wilcoxon rank-sum tests.*

2) Substance Use:

- a) Change in 30 day opioid abstinence (by ASI-lite self-report, TLFB and urine drug screen (UDS) confirmation) in the final 30 days of the 16 week trial compared to baseline (*binary; laboratory data and self-report*). *Analysis using rank-based methods as in outcome 2a.*
- b) Change in past 30day alcohol and other drug use by ASI-lite, TLFB, and UDS at 16 weeks, compared with baseline (*binary; laboratory data and self-report*). *Analysis using rank-based methods as in outcome 2a.*

3) Participant safety, as measured by:

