- a) Change in liver enzymes between baseline and 16 weeks or last lab measurement (*continuous; laboratory assay*). *Analysis via paired t-test, or analysis of change via ordinary least squares.*
- b) Any fatal and non-fatal opioid overdose at 16 weeks (*binary; medical record abstraction and self-report*). *Chi-squared test or logistic regression.*
- c) Change in Concise Health Risk Tracking score at 16 weeks compared to baseline (*continuous; self-report*). *Analysis via paired t-test, or analysis of change via ordinary least squares.*
- d) Proportion of participants assigned to XR-NTX who develop precipitated opioid withdrawal.

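### The overdose outcome window opens at screening, 1-4 weeks before randomization, so non-fatal overdoses that neither arm can have caused count as events

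*Protocol*

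**What the plan says.** Three places in the protocol set the window. Sections 5.2 and 17.2 both read "Any fatal and non-fatal opioid overdose between screening and week 16 visit", and section 8.2 reads "Any fatal and non-fatal opioid overdose between screening and week 16". Sections 8.2 and 17.2 label the outcome binary, with medical records and self-report as sources.

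Section 17.5 names the analysis, a chi-squared test or logistic regression, and words the outcome as "Any fatal and non-fatal opioid overdose at 16 weeks". That gives an end but no beginning. Section 17.6 analyzes participants in the arm to which they were randomized.

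On timing, sections 9.2 and 9.2.2 allow 1-4 weeks for screening and enrollment. Section 9.2.8 performs randomization once the baseline assessment is complete and expects it to "follow shortly after baseline assessments and final confirmation of eligibility". On data collection, section 15.2 states: "Non-fatal overdoses in the past 4 weeks will be assessed using a self-reported instrument used in previous studies at baseline and 16 weeks".

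**The concern.** A comparison of randomized arms should count only events that the assignment could have influenced. Here a non-fatal overdose in the weeks before assignment settles the participant's outcome as yes, and nothing after randomization can change it. Fatal events are not affected, because someone who dies during screening is never randomized.

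In expectation these events fall equally on both arms and pull the risk ratio toward 1. In one trial of at most 50 participants they may also fall unevenly by chance and move the estimate either way.

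The estimate has a purpose: Aim 4 Pilot Objective B in section 2.1 is to "Estimate effect size point estimates for secondary outcomes of HIV-1 RNA viral suppression, illicit drug and alcohol use, HIV care engagement, and safety", as input to the larger trial. Overdose is also a risk that the protocol itself raises for XR-NTX, in sections 4.1 and 23.1.5.5.

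**Working it through.** **1. The plan's own timeline.** Section 6.2 gives 17-24 weeks in the study. The phases in section 9.2 reproduce this: 1 + 0 + 16 = 17 and 4 + 4 + 16 = 24 weeks (screening, detoxification/induction, active treatment).

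**2. Share of the window before randomization.** With s weeks of screening and d weeks of induction, the share is s/(s + d + 16).
- Smallest: 1/(1 + 4 + 16) = 1/21 = 4.8%.
- Largest: 4/(4 + 0 + 16) = 4/20 = 20%.

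**3. Whether such events would be in the data.** They would. The non-fatal overdose form is given at baseline with a 4-week look-back (15.2), adverse events are collected from consent (22.4), and record abstraction covers overdose events (9.2.5). No section excludes events before randomization.

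**4. Effect on the risk ratio.** The protocol gives no overdose rate and no effect size, so the following are assumptions:
- a constant hazard h of 0.002 or 0.005 per week before randomization and in TAU;
- a hazard ratio HR for XR-NTX;
- t weeks from randomization to week 16, being 20 (4 + 16) or 16 (0 + 16);
- every event captured.

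True risks are 1 − exp(−h·t) in TAU and 1 − exp(−HR·h·t) under XR-NTX. Under the stated window they become 1 − exp(−h·(t + s)) and 1 − exp(−h·(HR·t + s)).

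Worked case, h = 0.005, HR = 0.5, t = 20, s = 4:
- True: (1 − e^−0.05)/(1 − e^−0.10) = 0.0488/0.0952 = 0.512.
- As defined: (1 − e^−0.07)/(1 − e^−0.12) = 0.0676/0.1131 = 0.598.

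In each cell below, the first figure is for h = 0.002 and the second for h = 0.005.

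| HR, t | True risk ratio | 1 week screening | 4 weeks screening |
|---|---|---|---|
| 0.5, 20 weeks | 0.505 / 0.512 | 0.529 / 0.537 | 0.589 / 0.598 |
| 0.5, 16 weeks | 0.504 / 0.510 | 0.534 / 0.540 | 0.605 / 0.612 |
| 2, 20 weeks | 1.961 / 1.905 | 1.914 / 1.860 | 1.797 / 1.746 |

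**5. Effect on the risk difference.** With q = 1 − exp(−h·s) as the risk before randomization, the difference is multiplied by 1 − q = exp(−h·s). This is 0.998 / 0.995 for 1 week and 0.992 / 0.980 for 4 weeks, so it keeps 98.0-99.8% of its size.

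**6. Counts among 50 participants.**
- Expected number with an event before randomization, 50q: 0.10 / 0.25 (1 week) and 0.40 / 0.99 (4 weeks).
- Chance of at least one such participant, 1 − exp(−50·h·s): 0.095 / 0.221 (1 week) and 0.330 / 0.632 (4 weeks).
- Expected number with an event after randomization, HR 0.5, 25 per arm, t = 20: 25 × (0.0392 + 0.0198) = 1.48 at h = 0.002, and 25 × (0.0952 + 0.0488) = 3.60 at h = 0.005.

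**The case against.** The best defense is that screening is this protocol's loose word for the pre-treatment reference point. Section 17.2 compares viral load and CD4 count with screening, although section 12.6 draws both after randomization. The CHRT item is worded from screening too, yet that scale is first given at baseline. Section 17.5, where the test is named, drops the word. Read with section 15.2, its phrase could mean the week 16 form alone, whose 4-week look-back contains no time before randomization for anyone who reaches that visit.

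The observation about loose usage is fair, but it does not remove the problem. For a change score, screening only names the reference value. For an any-event outcome, the start date decides which events count. Reading it as baseline would not help, because baseline also precedes randomization. A phrase with no start cannot override a window stated three times, and records and adverse event reports are sources besides the week 16 form.

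Several objections to the numbers stand as limits:
- The rate is applied to all 50 participants, although eligibility includes people with alcohol use disorder only, so the counts may be too high.
- The 4-week figures need every participant to spend the full 4 weeks in screening.
- Complete capture is assumed, whereas scheduled self-report covers only the 4 weeks before baseline and the 4 weeks before week 16. The baseline look-back can even reach back before screening. Incomplete capture does not necessarily soften the effect, however: if both forms counted, 4 of the 8 self-reported weeks would precede randomization.
- The hazard ratio is invented. The HR 2 row shows that harm would be diluted in the same way.

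It is also true that events before randomization are independent of arm and create no systematic difference, and that section 17.5 says "Any conclusions arising from secondary analysis must be regarded as hypothesis-generating only".

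**Conclusion.** The concern holds: the outcome is wrongly defined as written, and it is minor. That 4.8-20% of the stated window lies before randomization follows from the protocol's own phase lengths and needs no assumption.

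The size of the distortion does rest on assumed figures: 0.2-0.5% per week, constant, fully captured, in all 50 participants. On those, the risk ratio moves modestly with 1 week of screening and visibly with 4, while the risk difference is almost unchanged. Because only 1.5-3.6 participants are expected to have an event after randomization (HR 0.5, 20 weeks), even one with an earlier event can shift the estimate noticeably.

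The outcome is secondary and exploratory and no primary result is touched. The main reason to correct it is that the estimate, and possibly the definition, would carry into the multi-site trial.

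**What to change.** In sections 5.2, 8.2, 17.2 and 17.5, define the outcome as *any fatal or non-fatal opioid overdose from randomization to the week 16 visit*. State that the baseline non-fatal overdose form is baseline history, described by arm, and does not feed the outcome.

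This changes one phrase in four sections. It needs no new form or visit: the baseline form is already scheduled, and randomization is expected soon after it. The corrected window runs 16-20 weeks, depending on induction, and makes explicit that detoxification and induction time after randomization is counted.

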7.7 Rationale for CTP Selection

We will use the same site selection criteria for the pilot study as is planned for the multisite study. Sites will be selected for participation that have an adequate number of HIV-infected participants with untreated opioid use and/or untreated alcohol use disorders. In order to achieve target enrollment for this study, which is approximately 25 participants per site over 12 months of enrollment, we expect that participating HIV clinics will need to see $\geq 1,000$ unduplicated HIV-infected potential participants per year. This number is based on estimates of the percent of HIV-infected patients in 17 HIV clinics that were informally queried regarding participant availability (Appendix C), and experience of CHOICES investigators in enrolling subjects in the BHIVES study (Altice, Bruce et al. 2011). We have also included site selection criteria that attempt to limit site variability in treatment effects (e.g., capacity for prescribing ART regardless of CD4 count, presence of on-site addiction counseling services).

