For example, the highlighted row in the last – “paragraph” of **Table 17.2.1** shows that, if you assume that the pilot study recruitment rate is 2.28 participants per site-month (implying that the phase III randomized trial will likely require no more than 23 months to recruit), and if you choose to stop the pilot study after either 50 participants or 12 months of enrollment time (whichever comes first), and you choose to have two sites in the pilot study, then it is likely that the pilot study will recruit at least 48 participants and stop recruitment at 12 months. In this case, the 95% confidence intervals for $p(\text{init})$ and $p(\text{ret})$ will very likely be no wider than ± 0.22 and the prediction derived from the pilot study of the recruitment time for the subsequent randomized study will probably be off by no more than ± 3 months. This degree of imprecision appears acceptable for the pilot study.

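### The 18-month phase III plan needs 2.78 participants per site-month, not the stated 2.28, so no row of Table 17.2.1 represents the plan it starts from

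*Protocol*

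**What the plan says.** Under the sample-size heading in Protocol Section 17.2, the limit of 50 participants or 12 months is justified by reference to a later phase III trial. That proposal "assumes enrollment of 400 participants from 8 sites in 18 months, implying a recruitment rate of about 2.28 participants per site-month".

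The simulation behind Table 17.2.1 then explores "per site-month recruitment rate = (1.14, 2.28), number of sites = (1,2), and time period = (12 months, 18 months"). The notation list defines the rate as the "recruitment rate (participants per site-month) assumed for both the pilot study and the subsequent phase III randomized trial". It fixes the phase III size ("N = randomized trial sample size (assumed to be 400") and the number of phase III sites (8). Section 17.3 repeats 400 participants and 8 sites.

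Every row of the table uses 2.28 or 1.14, with 80th percentiles of phase III recruitment time of 23 and 46 months respectively. The worked example after the table takes the row with rate 2.28, two sites, at most 50 participants and at most 12 months. It describes the rate as "implying that the phase III randomized trial will likely require no more than 23 months to recruit". It expects at least 48 participants, a stop at 12 months, and half-widths no wider than 0.22.

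**The concern.** The rate is presented as a consequence of three numbers in the same sentence, and those numbers do not give it. Because the table was run at the stated rate, the slip passes into every row and into the worked example. The text therefore links one rate both to an 18-month trial and to a trial that will probably finish within 23 months, without saying that these differ.

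Two things are at stake. First, the table is the stated justification for the pilot's recruitment limits, so its starting assumption should be the one it names. Second, the rate that an 18-month trial with 8 sites would need appears nowhere in the protocol, although the pilot exists partly to inform the planning of that trial.

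**Working it through.** **Inputs.** From Section 17.2: phase III N = 400, S = 8 sites, 18 months; stated rate 2.28; simulated rates 1.14 and 2.28; chosen pilot of 2 sites, n ≤ 50, t ≤ 12 months. The protocol does not name the arrival model used for the table. I assume a Poisson process, which Section 17.3 also names for the recruitment rate.

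**Step 1: the rate.** Rate = N/(S × months) = 400/(8 × 18) = 400/144 = 2.78 per site-month; half of it is 1.39. The ratio 2.28/2.78 is 0.82, a shortfall of 18%.

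**Step 2: can 2.28 be recovered?**
- Counting in four-week or 28-day months gives 2.56, not 2.28.
- With the other two inputs held fixed, 2.28 would need about 328 participants (2.28 × 144), 21.9 months (400/(8 × 2.28)) or 9.7 sites (400/(18 × 2.28)).
- The protocol states none of these.

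**Step 3: reproduce the table at the stated rates.** The phase III time T follows a Gamma distribution with shape 400 and rate 8r. In the pilot, the number enrolled in t months at s sites is Poisson with mean r × s × t, capped at 50. The time to 50 participants is Gamma with shape 50 and rate r × s.

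| Quantity | Table 17.2.1 | Recomputed |
|---|---|---|
| 80th percentile of T, rate 2.28 | 23 | 22.8 |
| 80th percentile of T, rate 1.14 | 46 | 45.7 |
| 20th percentile of n, rate 2.28, 2 sites, 12 months | 48 | 48 |
| 80th percentile of time to 50, rate 2.28, 2 sites | 12 | 12.2 |

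The table really was run at 2.28 and 1.14. Some other cells differ under this simple model. For example, the 20th percentile of n for one site over 12 months at 2.28 is 23 against the printed 22, and the 80th percentile of the prediction error in the highlighted row is about 4.4 months against the printed 3. The point does not rest on those cells.

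**Step 4: phase III time at each rate.**

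| Rate | Mean T = 400/(8r), months | 80th percentile, months |
|---|---|---|
| 2.28 (stated) | 21.9 | 22.8 |
| 2.78 (from the plan's inputs) | 18.0 | 18.8 |
| 1.14 (stated half) | 43.9 | 45.7 |
| 1.39 (correct half) | 36.0 | 37.5 |

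At 2.28, eight sites expect 328 participants in 18 months, and the probability of reaching 400 by then is about 0.00007.

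**Step 5: the chosen pilot at each rate (2 sites, n ≤ 50, t ≤ 12).**

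| | 2.28 | 2.78 |
|---|---|---|
| Expected enrolment in 12 months without the cap (24r) | 54.7 | 66.7 |
| Probability of reaching 50 within 12 months | 0.756 | 0.985 |
| 20th percentile of n | 48 | 50 |
| 80th percentile of closing time | 12 months | about 10 months |

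**Step 6: precision.** The half-width per arm at p = 0.5 is 1.96 × √(0.25/(n/2)), with n reduced by 10% for retention. For n = 50 this gives 0.196 and 0.207; for n = 48 it gives 0.200 and 0.211. The table's own rows with n = 50 print 0.20 and 0.21, against 0.21 and 0.22 in the highlighted row. The change is about 0.01.

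**The case against.** The strongest defence is that little depends on the slip. The table calls the rate a state of nature that must be assumed, and it is valid conditional on the rates it prints. The 23 months stand beside every 2.28 row and again in the worked example, so an attentive reader can see that this rate does not deliver 18 months. The error is also conservative for the decision being justified: at 2.78 the cap is reached sooner and more surely. All of this stands. It limits the severity, but it does not make 400/(8 × 18) equal 2.28.

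Two stronger readings are tempting, and the protocol does not support them.

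- A reader might take 2.28 as the yardstick for the pilot, so that a pilot recruiting at 2.28 would falsely confirm an 18-month trial. No section sets such a threshold. Aim 3 estimates the rate, and Section 17.3 predicts phase III time by bootstrapping the observed inter-arrival times, with 400 participants and 8 sites; 2.28 does not enter. A pilot recruiting at 2.28 would lead to a prediction of about 22 months.
- A reader might divide the Section 7.7 target of "approximately 25 participants per site over 12 months of enrollment" to get 2.08 per site-month and count it as a third conflicting rate. That target is the pilot cap of 50 spread over two sites and 12 months, and it is used to size clinics. It is not a phase III assumption. At 2.28, two sites expect 54.7 participants in 12 months, so a capped target of 50 is compatible with that rate.

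**Conclusion.** The stated rate is wrong as written. The plan's own inputs give 2.78 per site-month, and the figure used is 18% lower. Table 17.2.1 and its worked example were run at the lower figure, so they describe a phase III trial averaging about 22 months, not 18, and the half-rate rows are displaced in the same way (36.0 months on average at 1.39 against 43.9 at 1.14).

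The pilot's limits, its precision and the planned Aim 3 analysis are not undermined. In the worked example, the description of stopping at 12 months would change to closing by about 10 months, and the other pilot figures improve slightly.

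The rate itself is plain division and needs no model. The percentiles and probabilities assume Poisson arrivals at a constant rate common to all sites, and the half-widths assume p = 0.5 with a normal approximation. This is a moderate correction to a planning figure and its supporting table.

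**What to change.** Choose one of two routes.

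1. If 18 months is the intended phase III assumption, replace 2.28 and 1.14 by 2.78 and 1.39, re-run Table 17.2.1, and update the worked example.
2. If 2.28 is the intended rate, keep the table and restate the assumption as 400 participants from 8 sites in about 22 months. Add a sentence noting that 18 months would need 2.78 per site-month.

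The first route costs a small simulation and a text edit; the second costs a text edit only. Neither changes enrolment, the stopping limits or any planned analysis.
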